3.6 Coding of Events and Medications

Medical history and AE verbatim terms will be coded using the Medical Dictionary for Regulatory Activities (MedDRA) using the latest version available at the time of study commencement. Terms will be coded to the full MedDRA hierarchy, but the system organ class (SOC) and preferred terms (PT) will be of primary interest for the analysis.

Prior and concomitant medications will be coded using the World Health Organization Drug Dictionary using the latest version available at the time of study commencement. Medications will be mapped to the full WHO-DD Anatomical Therapeutic Chemical (ATC) class level 4 and reported to class level 3 and 4 hierarchy, but PTs will be of primary interest in this analysis.

3.7 Treatment Groups

The following treatment group labels will be used for all summary outputs.

Part 1 (SAD):

This representation as below will only be used for the descriptive summary of concomitant medication, medical history and AEs and will not be based on feeding status:

- S1: CVN766 5 mg
- S2: CVN766 15 mg
- S3 Fasted: CVN766 45 mg
- S3 Fed: CVN766 45 mg
- S4: CVN766 125 mg
- S5 CVN766 250 mg
- Overall CVN766
- Overall Placebo
- S3 Fed: Placebo
- Overall

Note: Overall CVN766 is the pooled group of all participants with active treatment. The assessments for the participants with active treatments in Cohort S3 Fed: CVN766 45 mg condition are not counted in 'Overall CVN766', and they will be counted under 'S3 Fed: CVN766 45 mg'. 'Overall Placebo' is the pooled group of all participants with placebo. The assessments for the participants with placebo in Cohort S3 fed condition are not counted in 'All Placebo', and they will be counted under 'A3/Placebo/Fed'. In demographic and baseline characterises summary tables, Cohort S3 fed condition is not needed as appropriate.

Part 2 (MAD):

- M1: CVN766 45 mg
- M2: CVN766 125 mg
- M3: CVN766 250 mg
- Overall CVN766
- Overall Placebo

- Overall

Note: Overall CVN766 is the pooled group of all participants with active treatment.

Overall Placebo is the pooled group of all participants with placebo.

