2.1.1 Part 1: SAD is the single-dose regimen and Fasted- Fed Crossover

Approximately 40 healthy male or female subjects will be enrolled in 1 of 5 single-dose cohorts (designated as S1 through S5, respectively) in an ascending fashion. An optional Cohort 3a may be added in parallel to SC3 for additional safety and tolerability evaluation. Cohort S3a dose level will be consistent with Cohort S3 (45 mg planned) in a fasted condition only and without lumbar puncture, aligned with other SAD cohorts. Each cohort will consist of 8 subjects randomized to CVN766 or placebo, whereby 6 subjects will receive a single oral dose of CVN766 suspension, and 2 subjects will receive a matching placebo suspension under overnight fasted conditions. Sentinel dosing (1 subject to receive CVN766 and 1 subject to receive placebo) will be used in each cohort to ensure adequate safety and tolerability evaluation prior to administering CVN766 or placebo to the remainder of the subjects within the cohort. The planned dose levels will be 5, 15, 45, 125, and 250 mg CVN766. Each following dose level may be higher, lower, or remain the same as the preceding cohort. Additional cohort(s) may be added if deemed necessary by the SRG to fully characterize the safety and tolerability of CVN766. To assess the effect of food on CVN766 bioavailability in suspension formulation, the single-dose administration will be repeated in a single cohort (S3) after ingestion of a standardized high-fat, high-calorie meal. Once the safety of the S3 cohort dose level has been assessed, the S3 cohort subjects will return to the clinic (no sooner than 14 days after their prior dose, or at least 4 half-lives, has lapsed based on preliminary PK data, whichever is longer). They will receive the same dose as before, administered after ingesting a standardized breakfast. Subjects will finish at least approximately 85% of their breakfast within 30 minutes and receive an investigational product 30 minutes (\pm 5 minutes) after beginning the meal. Sentinel dosing will not be required for subjects returning to the clinic for the fed regimen. If the CVN766 PK parameters in the fasted S3 cohort reveal poor absorption with inconclusive results, the fed cohort will be deferred until a higher dose level.

[figure not shown]
On Day 1, subjects will undergo safety monitoring and PK sampling from blood plasma through 72 hours post-dose and, for cohort S3 (fasted) only, from CSF via lumbar puncture at 3 hours post-dose

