2.1.2 Part 2 MAD is a Multiple-Dose Regimen

Approximately 24 healthy male and female subjects aged 18 to 55 will be enrolled in 1 of the 3 multiple-dose cohorts (designated as M1 through M3, respectively) in an ascending fashion. The dose levels planned to be studied in the multiple-dose regimen are 45, 125, and 250 mg CVN766 for multiple-dose cohorts M1 through M3, respectively. Each multiple-dose cohort will consist of 8 subjects randomized to CVN766 or placebo, whereby 6 subjects will receive a daily oral dose of CVN766, and 2 subjects will receive matching placebo for 7 days. Dosing will be administered in the fasting state; the SRG can change this if exposure is higher in the fed state. The planned dosing duration for the multiple-dose cohorts is 7 days. However, the duration may be increased to \leq 14 days if preliminary PK data suggest steady-state will not be achieved within 6 days of daily dosing.

On Day 1 subjects, will undergo safety monitoring and PK sampling from blood plasma through 24 hours post-dose and on Day 7, will undergo safety monitoring and PK sampling from blood plasma through 72 hours post-dose. Additionally, PK samples will be collected on Days 3, 4, 5 and 6 prior to the next planned dose. For cohort M1, on day 7 only, subjects will undergo PK sampling from CSF via lumbar puncture at 3 hours post dose and PK sampling from urine over 24 h on Day 1 and Day 7. CSF samples may also be taken from M2 and M3 cohorts at the SRG's discretion.

Figure 1: Study Design

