2.3 Endpoints

Primary endpoint(s)

The primary endpoints of this study will be the following:

- Percentage of subjects who experience at least one treatment-emergent adverse event (TEAE)
- Percentage of subjects with abnormal and clinically significant (CS) safety laboratory test results at least once post-dose
- Percentage of subjects with abnormal and CS electrocardiogram (ECG) test results at least once post-dose
- Percentage of subjects with abnormal and CS vital sign measurements at least once post dose

Secondary endpoints(s)

- Single-dose plasma PK parameters of CVN766 including time to maximum plasma concentration (T_{max}), area under the plasma concentration-time curve from time 0 to 24 (AUC_{24}) and time 0 to infinity (AUC_{inf}), and terminal elimination half-life ($t_{1/2z}$) Multiple-dose plasma PK parameters of CVN766 including C_{min} , C_{trough} , C_{max} , AUC from time 0 to the end of dosing interval (AUC_t), terminal elimination half-life ($t_{1/2z}$), accumulation ratio (R_{acc}), time to steady-state ($T_{ss,max}$), steady-state C_{max} ($C_{max,ss}$), and steady-state C_{min} ($C_{min,ss}$) Single-dose and multiple-dose CSF concentrations and CSF: plasma ratios of CVN766

Other endpoints(s)

- Change from baseline in safety laboratory and ECG test results and vital signs.
- Additional plasma PK parameters of CVN766: CL/F or CL/F_{ss} and Vz/F or Vz/F_{ss}

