11.1 Adverse Events

All AEs including will be coded using latest MedDRA version. All AE summaries will be restricted to TEAEs only. AEs will be grouped by system organ class (SOC) and preferred term (PT) and summarized, by actual treatment group and overall. Summary tables will include the number of participants (%) experiencing an event and the number of events. Participants will be counted only once for each SOC and PT level; they will be sorted alphabetically and for PT tables only, they will be ordered with the highest first (categorical descriptive analysis).

For food effect cohort, an adverse event starting in one period and continuing into the next period is counted only in the onset period.

Assigned treatment	Definition
Treatment Period 1 (Fasting)	AE start date/time is on or after the dose date/time of treatment received in Period 1 and prior to the date/time of treatment received in period 2 (fed period) no matter when AE stops.
Treatment Period 2 (Fed)	AE start date/time is on or after the dose date/time of treatment received in Period 2 until the end of study.

For Part 1 (SAD) Cohort S3 food effect arm, TEAE will be further assigned to S3/Fasted (period 1) or S3/Fed (period 2) by using period 2 start date and TEAE's that start post first study drug administration of period 2 (Fed) will not be attributed to treatment during period 1 (Fasted). TEAE's that start post first study drug administration of period 1, but prior to first study drug administration of period 2, will be attributed to period 1 only. TEAEs that start post first study drug administration of period 1 (Fasted) and ongoing will be attributed to Onset period only

The TEAE summaries will include:

- Overall summary of TEAEs.
- TEAE summary by SOC and PT.
- TEAE summary of serious events by SOC and PT.
- TEAE summary by SOC, PT and Severity.
- TEAE summary by SOC, PT and relationship to study drug.
- TEAE summary of events leading to the study drug discontinuation by SOC and PT.
- Overall Frequency of TEAE by PT.
- Overall Frequency of related TEAE by PT.

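### Within each part, the fully punctured 45 mg TEAE column sits beside pooled placebo in which only 2 of 10 (SAD) or 2 of 6 (MAD) are punctured, and no summary separates puncture events

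*SAP*

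**What the plan says.** **Where the puncture happens.** SAP section 2.1.1 gives SAD sampling "for cohort S3 (fasted) only, from CSF via lumbar puncture at 3 hours post-dose". The optional cohort S3a repeats the S3 dose "in a fasted condition only and without lumbar puncture, aligned with other SAD cohorts", which confirms that the remaining SAD cohorts have none. For MAD, section 2.1.2 states: "For cohort M1, on day 7 only, subjects will undergo PK sampling from CSF via lumbar puncture at 3 hours post dose". It then allows CSF sampling in M2 and M3 if the SRG so decides.

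**How the columns are built.** Section 2.5 randomises 6:2 within every cohort. Section 3.7 and the shells then show one column per dose and, for each part, one placebo column: "Overall Placebo' is the pooled group of all participants with placebo". The only placebo condition shown separately is S3 Fed, which is the period without a puncture.

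**What is counted.** The first primary endpoint in section 2.3 is the percentage of participants with at least one TEAE, whatever its cause. Section 3.2 defines a TEAE by onset within 30 days of dosing; the shell footnotes define it as any event after first dosing. Both rules are purely time-based. Section 11.1 adds a "TEAE summary by SOC, PT and relationship to study drug", and the shell for that table offers only related or not related.

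**The concern.** Pooling placebo over cohorts gives a fair comparator for each dose only if the cohorts differ in dose alone. Here one cohort in each part also differs by an invasive procedure performed after dosing. Headache or back pain after a puncture counts as a TEAE and should affect drug and placebo participants in that cohort alike. Once placebo is pooled, the two arms no longer carry the same procedure burden in the dose-level columns.

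This has two effects. The 45 mg percentage is raised relative to placebo by something the drug did not do. The pooled placebo percentage is raised relative to the puncture-free doses, which then look a little better tolerated than they are. Tolerability by dose is the primary objective and is read from these columns.

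**Working it through.** **Counts from the SAP.** Section 2.4 gives 64 participants: 5 × 8 + 3 × 8 = 40 + 24 = 64, which reproduces. At 6:2 per cohort, pooled placebo is 5 × 2 = 10 in SAD and 3 × 2 = 6 in MAD.

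**Share punctured in each column** (the word subjects, in a double-blind design, is taken to include placebo):

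| Column | SAD | MAD, only M1 punctured |
|---|---|---|
| 45 mg (S3 fasted / M1) | 6/6 = 100% | 6/6 = 100% |
| Other doses | 0% | 0% |
| Overall Placebo | 2/10 = 20% | 2/6 = 33% |
| Overall CVN766 | 6/30 = 20% | 6/18 = 33% |

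**Model.** Let b be the background TEAE rate, equal in both arms, and q the probability that a puncture causes a TEAE. The SAP gives neither, so both are assumptions. With no drug effect, the TEAE probability is b without a puncture and L = 1 − (1 − b)(1 − q) with one. The expected difference between a dose column and pooled placebo is (1 − b) × q × (share punctured in the dose column − share punctured in placebo).

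**Example, b = 20%, q = 20%.**
- L = 1 − 0.8 × 0.8 = 36.0%.
- SAD placebo = (2 × 0.36 + 8 × 0.20)/10 = 23.2%. Excess at 45 mg = 12.8 points.
- MAD placebo = (2 × 0.36 + 4 × 0.20)/6 = 25.3%. Excess at 45 mg = 10.7 points.

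**Range over q at b = 20%** (points):

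| q | 45 mg, SAD | 45 mg, MAD | Puncture-free doses, SAD | Puncture-free doses, MAD |
|---|---|---|---|---|
| 10% | +6.4 | +5.3 | −1.6 | −2.7 |
| 20% | +12.8 | +10.7 | −3.2 | −5.3 |
| 30% | +19.2 | +16.0 | −4.8 | −8.0 |
| 40% | +25.6 | +21.3 | −6.4 | −10.7 |

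At b = 40% and q = 20% the 45 mg excess is 0.6 × 0.2 × 0.8 = 9.6 points (SAD) and 0.6 × 0.2 × 0.667 = 8.0 points (MAD).

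**Variants, b = q = 20%.**
- Puncture in M1 and M2: 0.16 × (1 − 4/6) = 5.3 points. In all three MAD cohorts: 0.
- S3a run and merged into the 45 mg fasted column: 0.16 × (6/12 − 2/12) = 5.3 points.
- Placebo participants not punctured: 0.16 × (1 − 0) = 16.0 points in either part.
- Overall CVN766 against Overall Placebo: 0 in both parts.

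**Chance of a misleading picture.** No test is planned, so take as a yardstick the probability that the 45 mg column shows an observed excess of 30 points or more when the drug does nothing. The threshold is this review's, not the SAP's. Exact binomial calculation, b = 20%:

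| q | Pooled placebo, SAD (6 v 10) | Pooled placebo, MAD (6 v 6) | Same-cohort placebo only (6 v 2) |
|---|---|---|---|
| 0 | 9.7% | 13.4% | 22.1% |
| 10% | 17.9% | 21.3% | 28.1% |
| 20% | 27.4% | 29.3% | 29.8% |
| 30% | 37.4% | 37.3% | 28.9% |
| 40% | 47.5% | 45.3% | 27.4% |

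In SAD at q = 20%, a background of 10% moves the figure from 4.9% to 26.6%, and a background of 30% moves it from 12.9% to 25.8%.

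The last column matters for the remedy. Same-cohort placebo removes the expected bias, but with two participants it is noisier than pooled placebo for q up to 20%.

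**The case against.** Pooling placebo over cohorts of two is a deliberate gain in precision, and the table above shows that undoing it would often do more harm than good. That objection stands and shapes the fix.

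It can also be said that the detail is recoverable. TEAEs are tabulated by preferred term and by relationship to study drug. The AE listing has verbatim term and onset time, the CSF listings have collection times, and cohort-level placebo labels are defined for listings. This helps only in part. Relationship to study drug does not identify procedure events, and no listing changes the primary percentage. As shelled, the AE and CSF listings name only active-dose groups, and the CSF listings use the PK set, which requires a measurable plasma concentration. Placebo puncture times would therefore probably not appear there.

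A reader might go further than the SAP supports in five ways:

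- **That puncture events will be reported as a drug effect.** Section 3.3 is descriptive. The TEAE shells show counts side by side, with no dose-versus-placebo difference, test or decision rule. The events can be misread; the plan does not itself draw the conclusion.
- **That MAD is biased whatever happens.** The M1 puncture is on Day 7, and section 2.1.2 leaves M2 and M3 to the SRG. The MAD artefact shrinks or vanishes if they are sampled.
- **That a true dose trend from M1 to M3 is flattened or reversed.** Flattening is the direction of the bias if only M1 is punctured. Whether it matters, let alone reverses a trend, depends on rates the SAP does not give.
- **That S3a will be merged with S3.** S3a is optional and the SAP never says so. It simply has no treatment label in section 3.7 or the shells. The shells' clause on extra dosing groups does not clearly cover a cohort that repeats an existing dose.
- **That a fasted-versus-fed safety comparison is spoiled.** The puncture does fall only in the fasted period, but the planned food-effect analysis is of PK parameters.

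**Conclusion.** The imbalance is real and follows from the SAP's own design: puncture exposure of 100% at 45 mg against 20% (SAD) or, if only M1 is punctured, 33% (MAD) in the placebo column beside it. The shares rest on one assumption, that placebo participants are also punctured; if they are not, the gap is wider. The direction needs only some puncture-related events. The size is illustrative because b and q are assumed.

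The SAD part holds as the plan stands. The MAD part is conditional on the SRG's decision. The point concerns how the dose-level TEAE columns are read. It leaves the pooled active-versus-placebo summary intact and does not invalidate the descriptive analysis. It is worth correcting before unblinding because the correction is cheap.

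**What to change.** In SAP sections 3.7 and 11.1 and the TEAE shells:

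1. Keep the pooled placebo and Overall columns. Add a supplementary row giving the primary TEAE percentage with events attributed to the lumbar puncture excluded. Decide attribution before unblinding, from the verbatim term and onset after the recorded CSF collection time, with the same written rule for both arms. This does not depend on a procedure-causality field, which the SAP does not show to exist. If attribution is accurate, the 30-point yardstick returns to its no-puncture level at 20% background: 9.7% in SAD and 13.4% in MAD.
2. Footnote the columns whose cohorts were punctured, including M2 or M3 if the SRG adds them, and state the number punctured within Overall Placebo.
3. If S3a is run, show it as its own column, 45 mg (Fasted, no LP), not under 45 mg (Fasted). It would then be a puncture-free 45 mg group.
4. Do not make the two-person punctured placebo groups the main comparator; show them descriptively at most.

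The cost is one extra TEAE row, some footnotes, one column if S3a is run, and a blinded attribution step. No new participants are needed. The downside is that attribution may misclassify a few non-specific events such as headache, so the row should stay supplementary to the unadjusted percentage.

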4. ANALYSIS SETS

In this study 3 analysis populations are defined: Safety and PK.

Furthermore, any additional exploratory analysis not identified in the SAP will be identified in the final CSR as exploratory post hoc analyses, including analyses for additional study populations or subgroups of interest.

4.1 Population Descriptions

Safety Set

The Safety Analysis Set will consist of all subjects who are enrolled and receive study drug. Subjects in this analysis set will be used for demographic, baseline characteristics, and safety summaries.

PK Set

The PK set will consist of all subjects who receive study drug and have at least 1 measurable plasma concentration.

If any subjects are found to be non-compliant in dosing schedule or with incomplete data, a decision will be made on a case-by-case basis as to their inclusion in the analysis but will be presented in the subject listings.

5. PARTICIPANT DISPOSITION AND ANALYSIS POPULATIONS

Participant disposition and analysis population analysis will be based on Safety population. Participant disposition and analysis populations will be summarized descriptively as described in section 3.1 (categorical descriptive analysis).

Participant Disposition

Participant disposition will include the number of participants who completed the treatment/study as planned, participants withdrawn from the treatment /study, as well as the primary reason for early termination. Participant disposition will be summarized descriptively.

Analysis Populations

The number of participants included in each study populations will be summarized descriptively.

In addition, the inclusion of each participant into/from each of the defined analysis populations will be presented in the by-participant data listings.

6. PROTOCOL DEVIATIONS

Protocol deviations will be presented for each participant in the by-participant data listings, sorted by study part, dose level and participant ID based on the All-Enrolled population.

Prior to database lock, all protocol deviations will be reviewed by medical monitors and assigned a status of importance if qualifying as such.

Protocol deviations, including Minor and Important protocol deviations, will be categorized as noted in the Protocol deviation management plan version 4.0 amendment 3 dated 19 May 2022.

All protocol violations that impact the safety of the patients and/or the conduct of the study and/or its evaluation will be reported. These include:

- Patients who are dosed on the study despite not satisfying the inclusion criteria
- Patients who develop withdrawal criteria whilst on the study but are not withdrawn
- Patients who receive the wrong treatment or an incorrect dose
- Patients who receive an excluded concomitant medication
- Deviations from GCP.

The identification of these and other CSR-reportable deviations will be based on the inclusion/exclusion criteria or other criteria presented in the protocol.

7. DEMOGRAPHIC AND BASELINE INFORMATION

Demographic and baseline information analysis will be based on Safety population. Demographic and baseline information will be summarized descriptively as described in section 3.1.

7.1 Demographics

The following demographic parameters will be analyzed:

Continuous descriptive analysis:

- Age (years)
- Height (cm)
- Weight (kg)
- BMI (kg/m²)

Categorical descriptive analysis:

- Sex
- Childbearing Potential
- Race
- Ethnicity

7.2 Medical /Surgical history

Medical / Surgical history will be coded using MedDRA® and will be presented in the by-participant data listings. Medical history to be obtained will include determining whether the subject has any significant conditions or diseases that stopped at or prior to signing the ICF.

7.3 Hepatitis panel and HIV Antibody Test

Hepatitis B Antigen (HBsAg), Hepatitis C Antibody (HCVAb), and Human Immunodeficiency Virus (HIV-1/HIV-2 Antibody) results will be presented in the by-participant data listings.

7.4 Alcohol, Urine Drug & Cotinine Screen Test

Urine Drug Test results will be presented in the by-participant data listings.

7.5 Follicle stimulating hormone (FSH) Test

FSH Test results will be presented in the data listings.

7.6 Pregnancy Test (Serum and Urine)

Serum and urine pregnancy test results will be presented in the by-participant data listings.

8. TREATMENT EXPOSURE

All study drug administration information (study drug administered (Yes/No), reason not administered, dose administered (mg), date and time of administration, vomiting (Yes/No), lot number/ bottle Number and date/time of first/last meal will be presented in the by-participant data listings under the Safety Set.

9. PRIOR AND CONCOMITANT MEDICATIONS

Concomitant medications will be coded using the most current version of the World Health Organization Drug Dictionary (WHO-DD) and summarized by Anatomical Therapeutic Chemical (ATC) class Level 3 and PT and will be presented alphabetically as noted in section 3.1 (categorical descriptive analysis) using Safety Set. All concomitant treatments, blood products, as well as nondrug interventions received by patients from screening until the end of study visit will be recorded on the eCRF.

The number and percentage of subjects using at least one concomitant medication will be displayed together with the number and percentage of subjects using at least one medication within each therapeutic class (ATC-Level 3) and preferred name A participant who used the same medication on multiple occasions will only be counted once in the specific category (PT). These will be summarized under the Safety population for dose levels defined in [section 3.5](#) Prior medications will be presented in the by-participant data listings.

For food effect cohort, a concomitant medication starting in period 1 (Fasted) and continuing into the next period (Fed) is counted only in the onset period.

